		9.2 Clarification of PHI	
		9.2;10.1; 21.1 Updated language for consistency to Study Information Letters from Study Information and Letters/Information Letter 16.1 Clarification of consistency regarding	
		benefits of patient participation	

		23.3 Updated enrollment log to show PHI will be temporarily kept and reflected that change in section 9.2 noting an enrollment log will be kept containing PHI and will be destroyed at the end of study 25.0 Virtual visits will not be recorded, so that box was not checked	
		31.0 Clarified that a CM approved method will be used	
3	March 2023	Updating formatting throughout the document (font, margins) for consistency, survey types (section 11), accelerometer type (section 5.3, 10.1, 15.1, 25.1, 27.1), study objectives (2.0), corrected references for assessments (11, 34). Updated section 6 to accurately describe the Nudge system. Updated section 7 to include a CGM eligibility requirement for data	Yes
		collection requirements	

Updated Section 10 to clarify the activity calendar would just ask about scheduled physical activity and included information about the sleep diary. Included the sleep diary in section 11.

Updated section 31 and 32 with information about collaborators & multi-site setup.

Updated section 23.3 to clarify that collaborators will have access to patient telephone numbers and addresses and clarified location of the Nudge server

Updated information letter with the location of collaborating sites, surveys, changed "Garmin" to "actigraph" in the study calendar, and made the information more clear.

Updated the
Treatment
Satisfaction survey to
correct some
grammatical errors
(question 4 did not
have the correct
"Yes, Definitely"
response)

4	May 2023	Updated section 5,	Yes
7	1viay 2023	10, and 18 to include actiwatch recording (instead of accelerometer)	
		Updated study population and inclusion exclusion criteria to 13 YOs to streamline study start up. Updated payment plan per new guidelines.	
		Updated section 32 to include KUMC student who will be working on the protocol.	
		Updated information letters to include information on the student worker, update the accelerometer to actiwatch, clarify daily surveys, clarify the payment schedule, and provide next steps after study enrollment	
		Edited survey request emails to include Nudge in the subject line and message	
		Edited Baseline survey to updated Q 9 in the TSRQ and 13 in the TSRQ-D to include a number box for recording the subject response	

	Added "Cell phone number" to Baseline survey to help with contacting participants	
	Corrected answers 17- 21 for the POMs in Nudge Day 1-7	
	Added in messages for EMA surveys for Nudge Days 1-7	
	Added surveys sent to parents or patients to confirm eligibility and receive information letter	
	Created a letter to link participants to a survey to alert the study team that the study devices were received	
	Created the study device received survey	
	Edited EMA surveys to the correct survey title (EMA day 1 A, etc.), and include time question (AM vs. PM)	
4.1	Updating KU & Kansas University term to University of Kansas in and KUMC to University of Kansas Medical School for clarity in sections 23.3 and 32. These corrections were also made in the information letters.	Yes
4.2	Updated University of Kansas Medical School to University of Kansas	Yes

		Medical Center in section 32. These corrections were also made in the information letters. And removed [name] email from intro (typo) And corrected reference 13 & 19 (typos)	
4.3		Corrected and confirmed names of Kansas University at Lawrence and KUMC to keep institution responsibilities clear. This was in section 23.3 and 32. Also updated the study calendar in section 5.3 to correct HbA1c to "SOC" and Device uploads to "Daily" timeframes. Calendars in ICFs have also been updated.	Yes
4.4	August 2023	Added in insurance type as piece of information recorded in section 25 (and table in section 25) Added in to study information letter Updated 25.1 demographics list, and incorporated the Diabetes Data Dock	Yes

at CMKC and using the health API and diabetes data mart, and specifying Diabetes Data Dock for data storage in section 28.1

Also updated 25.1 to specify the Diabetes Data Dock will verify/ extend demographics data listed in the list of data collected in demographics surveys

Added payment for exit survey completion section 18.1

Updated recruitment methods to reflect primarily virtual recruitment section 9.2 and 10.1

Updated section 28.1 to clarify the study records will be stored per CM policy, and a data scientist assigned to the study will have access to the study information

Also updated the RTDA and Diabetes Data Mart to diabetes Data Dock, as this is the new title of the data processing system.

Information letter: Added in insurance type as information

		collected, the payment for the Exit survey, the study contact information, and updated the language coordinators connect to for participant to connecting to the Garmin Health API app. Added [name] as the lead coordinator	
5	February 2024	See Summary of Changes document	Yes
5.1	March 2024	Section 21 updated for clarity Section 22 language added to reflect process of assent capture	Yes
5.2	March 2024	Section 9.1 updated to reflect use of self-referral Section 21 updated to include applicable study groups	
5.2.1	March 2024	Section 32 Nemours Children's spelling error corrected	

1.0 Study Summary 1.1 Synopsis

Study Title	Novel mHealth Physical Activity Intervention for Adolescents and Young Adults with Type 1 Diabetes (T1D)
Study Design	Non-randomized, longitudinal cohort study to pilot an intervention
Primary Objective	To evaluate feasibility and initial efficacy of a novel mHealth intervention to promote physical activity in youth and young adults with T1D
Secondary Objective(s)	To examine if increasing minutes of daily PA in youth and young adults with T1D promotes more optimal HbA1c levels.

Research Intervention(s)/ Investigational Agent(s)	Novel mHealth intervention (i.e., uses daily two-way text messaging) designed to promote physical activity in adolescents and young adults.
IND/IDE #	NA
Study Population	Patients 13.00 to 21.99 with T1D
Sample Size	250
Study Duration for Individual Participants	4.5 months (timeframe between standard of care visits)
Study Specific Abbreviations/F Definitions	T1D= Type 1 diabetes HbA1c= glycated hemoglobin PA= physical activity YA(s) = young adult(s) MVPA= moderate to vigorous physical activity NUDGE= Network Underwritten Dynamic Goals Exchange EMA= ecological momentary assessment

2.0 Objectives

2.1 Purpose, specific aims or objectives: *Describe the purpose, specific aims, or objectives. If more than one objective be sure to list separately.*

The study objectives are to examine feasibility of a novel mHealth intervention to promote physical activity (PA) in youth and young adults (YAs) with type 1 diabetes mellitus (T1D). The study objective is to examine initial efficacy of a novel mHealth intervention to promote PA in youth and YAs with T1D.

2.2 Hypotheses: *State the hypothesis to be tested.*

AIM 1: Test feasibility and initial efficacy of a novel mHealth intervention to promote PA in youth and YAs with T1D.

Hypothesis 1: Our application of a novel mHealth intervention to promote PA in youth and YAs with T1D will show feasibility based on ≥50% of daily text messages exchanged between youth and the intervention bot.

Hypothesis 2: Our application of a novel mHealth intervention to promote PA in youth and YAs with T1D will show initial efficacy based on the threshold of achieving at least a medium effect size for participant's daily PA.

AIM 2: Evaluate if increasing minutes of PA in youth and YAs with T1D promotes more optimal HbA1c levels.

Hypotheses 3: Youth and YAs with T1D who increase their daily PA based on our novel mHealth intervention will also show an improvement in their HbA1c levels.

3.0 Background

3.1 *Describe the relevant prior experience and gaps in current knowledge.*

There are approximately 200,000 children in the US (0-18 years) living with type 1 diabetes (T1D) and nearly 18,000 children diagnosed annually, 1-3 making T1D the third most common chronic illness of childhood. T1D requires a rigorous, complex, and time-consuming daily self-management routine in order to achieve blood glucose levels that approximate the normal range. One component of this self-management routine is daily PA. The American Diabetes Association (ADA) recommends that youth with T1D achieved at least 60 minutes of moderate to vigorous physical activity (MVPA) daily. Moreover, in a recent consensus statement, the authors note a number of unique benefits to youth with T1D who achieve this daily MVPA target, including reduced glycated hemoglobin (HbA1c) levels and improved cardiovascular disease risk profiles, endothelial function, and blood lipid profiles (viz., triglycerides and total cholesterol). Yet, despite these health benefits, most studies suggest that youth with T1D do not meet daily recommendations for MVPA.

There are examples of previous PA-focused interventions for youth with T1D, but only a few of these interventions focused on increasing daily PA in youth's daily lives (versus targeting periodic structured PA training sessions). Moreover, there are no examples of PA-focused interventions for adolescents and YAs with T1D that use an mHealth approach, despite the high likelihood that adolescents and YAs might find this treatment approach more feasible and acceptable than a traditional in-person or structured exercise-based intervention. Specifically, in-person exercise-based interventions may have multiple barriers for youth with T1D as these interventions may be time intensive, burdensome, and expensive, with most requiring participants to attend weekly sessions over multiple months. Additionally, face-to-face interventions could be difficult to disseminate if major segments of the population have limited access to healthcare resources necessary to deliver the treatment ¹¹ mHealth interventions include interactive and communication technologies to improve health or health care. Eighty-eight percent of teens own or have access to a cell phone, ¹² indicating that mHealth interventions in the form of a mobile phone platform would be widely accessible to adolescents. Further, previous literature suggests that mHealth interventions ¹³ have a small but significant

effect on changing health outcomes in pediatric populations.¹³ However, most mHealth interventions for PA do not utilize behavioral change techniques that are based on theory or are empirically supported. ¹⁴ Incorporating both theory and empirically based techniques would likely increase the effectiveness of mHealth physical activity interventions. ¹⁵

3.2 *Describe any relevant preliminary data.*

Cybernetic control theory is a model of self-regulation that postulates individuals monitor their current performance compared to a goal or standard. A negative feedback loop operates to reduce any discrepancy between one's current performance and a set goal. Key behavioral change techniques consistent with this model include goal setting, self-monitoring, feedback, and goal-review. Prior literature has shown interventionist employing control theory behavioral change techniques are effective in changing PA behaviors. ¹⁶ Specifically, in a meta-analysis of PA interventions, researchers found that PA interventions that included combinations of self-monitoring with other behavioral change techniques from control theory (i.e., goal setting, feedback) were significantly more effective than interventions that did not include these combinations. ¹⁶

Previous literature in youth also indicates that self-monitoring is a key behavioral change strategy that should be included in mHealth physical activity interventions. ¹⁵ For example, in a recent review of mHealth interventions, researchers found self-monitoring was a crucial component in changing exercise behaviors in adolescents. ¹⁵ Currently, the majority of mHealth text messaging interventions for PA consist of static or reminder-based text messages. ¹⁷ Developing adaptive interventions, which include personalized feedback and intervention content through text messaging, may improve the efficacy of an mHealth PA intervention for adolescents. Specifically, ninety percent of adolescents exchange text messages daily. ¹² This suggests that an mHealth PA intervention utilizing text messages may be an effective way to communicate with adolescents.

3.3 Provide the scientific or scholarly background for, rationale for, and significance of the research based on the existing literature and how it will add to existing knowledge.

Rationale

Here, we propose to pilot test the application of a novel and brief mHealth intervention to promote PA in youth and YAs with T1D. Our intervention, NUDGE (Network Underwritten Dynamic Goals Exchange), ¹⁸ utilizes intervention strategies consistent with control theory that have been shown to increase physical activity by encouraging participants to set daily physical activity goals, actively self-monitor progress, receive feedback, and review/revise their future goals. ^{18, 19, 20} Further, the adaptive features of NUDGE allow participants to set individualized physical activity goals, within a predefined range (i.e., +/- 15 minutes) of their last self-monitored physical activity value and receive immediate feedback. In a previous trial of NUDGE in adolescents without a chronic health condition (n=20 received NUDGE, n=20 controls), we found a medium effect size of NUDGE on adolescents' PA (d=0.63) and a large effect size on

adolescents' minutes of sedentary behavior (d=0.87). Therefore, NUDGE appears to be initially feasible and effective for youth and YAs in general. Prior data suggests a logical next step may be to pilot test NUDGE in a sample of youth and YAs with T1D, a vulnerable patient population with below target levels of daily PA.

Also, see above mentioned literature studies and rationale in 3.1 and 3.2 for additional background, significance of existing literature, and rationale.

4.0 Study Endpoints

4.1 *Describe the primary and secondary study endpoints.*

The primary endpoint is to increase daily PA in pediatric patients with T1D. The secondary endpoint is to improve HbA1c levels in pediatric patients with T1D.

Initial Efficacy Assessment. We will evaluate initial efficacy based on change in minutes of daily MVPA in adolescents from baseline to post-treatment, change in minutes of daily SB in adolescents from baseline to post-treatment, and change in HbA1c levels in adolescents from baseline to post-treatment.

4.2 Describe the primary and secondary safety endpoints. **NA**

5.0 Study Design

5.1 Study Design: *Describe and explain the study design.*

We propose to pilot NUDGE in youth with T1D and look at treatment effects after at least 3 months. We anticipate the entire pilot study will last 12 months.

5.2 Schema: a schema is a representation of your study design in the form of an outline or a model. Including a schema is not a requirement but can be valuable tool in the presentation of your study to the IRB. Consider adding a diagram that provides a quick "snapshot" of the study.

Study Visit Procedures

5.3 *Table of Events*

	Consent	Visit 1 (Day	Day 25	Visit 2 (Day	Day 85	Visit 3 (Day	Daily	PRN (SOC)
	(Day -10 to	1 to 7)		30 to 37)		90 to 97)		
	-5)							
I/E Criteria	X							
E-Consent PAC	Х							
Baseline Survey	Χ							

Medical Chart	Χ							
Review for								
demographics								
Medical Records	Χ							X
– HbA1c								
Medical Records	Χ						X	
device uploads								
PA Calendar	Χ							
PA Goal Set	Χ						X	
Actiwatch	Χ		Х		X			
Shipment								
Actigraph	Χ		X		X			
Shipment								
Participant		X		X		X		
wears Aciwatch								
Participant		Х		Х		Х		
wears Actigraph								
Participant to co		Х		X		Х		
mplete								
EMA REDcap Sur								
vey (7 days,								
4x/day)								
Treatment						X		
Satisfaction								
Survey and Post								
Survey								

All questionnaires are outlined in Section 11.0.

6.0 Study Intervention/Investigational Agent

6.1 Description: Describe the study intervention and/or investigational agent (e.g., drug, device) that is being evaluated.

NUDGE mHealth intervention. NUDGE is a brief mHealth text messaging intervention designed to promote activity in adolescents by allowing them to set, monitor, and receive feedback on daily PA goals through text message. The only PHI required to be entered is a phone number to receive the text messages. Messages in the Nudge bot are sent via the Twilio server

and stored in the SQL firewall protected server. At baseline, the participant will choose a time of day when he/she would like to receive a text message to set a daily PA goal. Plus, he/she will receive a text message to set an initial goal for daily MVPA that is between 15-60 minutes. The NUDGE bot will store this goal in a study-specific database overnight. Then, at the predetermined time the next morning, the NUDGE bot will send a text message reminding the participant of his/her stored goal. In addition, later in the same day, the NUDGE bot will send a text message to prompt the participant to self-monitor his/her PA and share this number (in minutes per day) via a text message. Once NUDGE receives this response, it will store the response in a study-specific database in order to compare it to the previously obtained goal value (from the day before). The NUDGE bot will then provide feedback to the participant indicating whether or not he/she met the predefined goal, and it will request a new goal. At this point the NUDGE bot will only accept goal values that are between an investigator defined range (e.g., 75-125%) of the last self-monitored PA value, so that future performance is tied to past performance and participants cannot set goals that are too high or too low to be useful. Participants with T1D will engage in this intervention for up to four and a half months.

- **6.2 Drugs or Biologics:** If this study involves the administration or dispensation of a drug or biologic, complete the table below. **NA**
- 6.3 Medical Devices. If this study involves the evaluation of the safety or effectiveness of a medical device (including mobile medical apps), or the use of medical device with a Humanitarian Use Device designation, include the following information: NA
- **6.4 Behavioral Intervention:** *If this study involves a behavioral intervention, describe the intervention in detail. Be sure to address whether the intervention is experimental or considered to be an accepted standard.*

This behavioral intervention includes the use of a mobile app to modify PA. Participants are allowed to set their own goals within guidelines. These goals will be monitored by the app and provide personalized feedback to promote PA. This study explores cybernetic Control Theory, a conceptual model to attain PA goals in pediatric patients which utilizes self-monitoring, feedback, goal setting, and goal review to modify behavior as noted in Section 3.0 of this protocol under the sub-heading 3.3.

SUBJECT MANAGEMENT

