8.0 Local Number of Subjects

8.1 Indicate the total number of subjects or charts to be enrolled locally as well as the accrual goal. If the study includes multiple groups or cohorts, be sure to describe the number of subjects required for each cohort. If one of the groups includes a chart review, each chart is considered a subject and needs to be reflected in the numbers below.

Target sample size is one group of 50 participants.

	Group 1	Group 2	Totals
Accrual Goal:	50	NA	
The number of evaluable subjects/charts you are targeting for the required			

andraint for the		
endpoint for the		
study.		
This number		
typically is based		
on statistical input		
such as a power		
analysis.		
_		
Anticipated	70	
Anticipated	/0	
Enrolled/Consented:		
This is the		
number reported		
at Continuing		
Review.		
Estimated number		
of subjects/charts		
that you anticipate		
you will need to		
enroll in order to		
meet your accrual		
goal above.		
This can generally		
be calculated as		
accrual goal +		
number of		
anticipated screen		
failures + number		
of potential		
withdrawals/drop		
outs.		
A (1.70	250	
Anticipated Pre-	250	
	250	
Screened (if applicable):	250	
Screened (if applicable): Estimated number	250	
Screened (if applicable): Estimated number of subjects/charts	250	
Screened (if applicable): Estimated number of subjects/charts you anticipate you	250	
Screened (if applicable): Estimated number of subjects/charts you anticipate you will screen prior to	250	
Screened (if applicable): Estimated number of subjects/charts you anticipate you will screen prior to	250	
Screened (if applicable): Estimated number of subjects/charts you anticipate you will screen prior to obtaining	250	
Screened (if applicable): Estimated number of subjects/charts you anticipate you will screen prior to obtaining permission/assent/	250	
Screened (if applicable): Estimated number of subjects/charts you anticipate you will screen prior to obtaining permission/assent/consent.	250	
Screened (if applicable): Estimated number of subjects/charts you anticipate you will screen prior to obtaining permission/assent/consent. For example, if	250	
Screened (if applicable): Estimated number of subjects/charts you anticipate you will screen prior to obtaining permission/assent/consent. For example, if your study	250	

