Baseline Surveys will be sent to participants via REDCap after informed e-consent PAC is completed. This will include Demographics, Treatment Self-Regulation Questionnaire (Exercise), Treatment Self-Regulation Questionnaire (Diet), Perceived competence for Exercise Questionnaire, Social Support for Exercise Questionnaire, (Family), Social Support for Exercise (Friends), Physical Activity Self-Efficacy Questionnaire, and Physical Activity Attitudes Questionnaire, Power of Food Scale, and Pediatric Quality of Life (PedsQL) Parent Report.

We will collect an objective measure of participants' MVPA based on wrist-worn actigraphs and wrist-worn actiwatches. Youth and YAs with T1D who consent to participate will receive a GT3X actigraph and instructions how to share the data from their GT3X actigraph with the study team. Participants will also receive an actiwatch (Garmin Vivosmart 4 or higher as an additional measure of MVPA. We will use age-appropriate guidelines to identify and calculate daily minutes of MVPA.

We will ask participants to complete a PA calendar in order to track their scheduled PA. This activity calendar will be completed in REDCap. Participants will also answer an open-ended question "What would you like to set your initial baseline PA goal as in minutes?" to help to anchor PA goals for the NUDGE intervention.

Participants may complete questionnaires outlined in section 11.0 electronically with the survey links sent via email or text using Twilio. We will set up the distribution of the EMA REDcap Surveys to be completed 4 times per day with family and/or participants for seven days for the initial 7-day assessment with the actigraph and actiwatch. The EMA Survey includes Negative Affect Scale for Children Questionnaire, Latent Mood Questionnaire, Environment Questionnaire, and a sleep diary. The actigraph and actiwatches will be shipped within 10 days to participants with instructions on how to use both as well as how to return the devices at the end of seven days.

Visit 2:

Set up distribution of the EMA REDcap Surveys with family and/or participant 4 times per day for seven days. The actigraphs and actiwatches will be shipped within 10 days to participants with instructions on how to use the devices as well as how to return the devices at the end of seven days.

Visit 3:

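### Nothing holds NUDGE messaging until the first device week ends, so the only possible activity baseline may be partly or wholly treated

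*Combined protocol and SAP*

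**What the plan says.** **Design and contrast.** The synopsis (1.1) describes a "Non-randomized, longitudinal cohort study to pilot an intervention", and 8.1 says "Target sample size is one group of 50 participants". Section 4.1 bases initial efficacy on change from baseline to post-treatment in daily MVPA, sedentary behaviour and HbA1c. Section 27.1 plans multilevel analyses and takes at least a medium effect size as the threshold for MVPA. It defines neither a baseline period nor an intervention start.

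**Device weeks.** Table 5.3 places device wear at Day 1-7, Day 30-37 and Day 90-97. Section 10.1 has the devices returned after each seven days, and the payment table in 18.1 pays for 21 wear days.

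**NUDGE timing.** Section 6.1 says that at baseline "he/she will receive a text message to set an initial goal for daily MVPA that is between 15-60 minutes". It goes on: "Then, at the predetermined time the next morning, the NUDGE bot will send a text message reminding the participant of his/her stored goal". A self-monitoring prompt follows later that day, and then feedback and a request for a new goal. Table 5.3 marks PA Goal Set in the Consent column (Day -10 to -5) and in the Daily column, with no first day for the latter. Section 10.1 adds an open-ended goal question asked "to help to anchor PA goals for the NUDGE intervention", placed after the REDCap activity calendar and without a date.

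**Duration.** Section 6.1 states: "Participants with T1D will engage in this intervention for up to four and a half months". The synopsis gives the same 4.5 months as the whole individual participation. Section 5.1 intends to "look at treatment effects after at least 3 months".

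**The concern.** With no control group, the before-after change is the only efficacy contrast, and it needs a before. Goal setting, self-monitoring and feedback are the active ingredients of NUDGE (3.2, 3.3). If they run before or during Day 1-7, the baseline already holds part of whatever effect they have, and the measured change is probably too small against the medium-effect threshold. Section 27 says that the pilot exists to supply power calculations for a larger study, so the distortion would carry forward.

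A multilevel model cannot repair this. If all seven days are exposed, an untreated activity level was never recorded. The other activity sources do not replace it: the calendar lists scheduled activity only, and the minutes texted to the bot exist only once NUDGE is running.

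The start day could also differ between participants, since staff could follow 5.3, 6.1 and 10.1 faithfully and begin messaging before, during or after the wear week.

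**Working it through.** **1. Device days.** Three wear weeks (5.3) of 7 days (10.1) give 3 x 7 = 21, which matches the 21 paid days in 18.1. Cross-checks: EMA payments are 3 x 7 x 4 x $2 = $168, and the total is 50 + 105 + 100 + 168 + 100 + 75 + 50 = $648, both as stated. The printed windows for Visits 2 and 3 span eight calendar days each, but this does not affect the count of untreated days.

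**2. Which days can be untreated.** Visits 2 and 3 fall while NUDGE is running, so untreated device days can come only from Day 1-7.

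**3. Count by start day.** Let the first goal text arrive on Day g. By 6.1 the first reminder comes on Day g + 1. Untreated device days are the wear days before Day g + 1.

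| First goal text | First reminder | Day 1-7 under NUDGE | Untreated, of 21 |
|---|---|---|---|
| Consent, Day -10 to -5 | Day -9 to -4 | 7 | 0 |
| Day 1 | Day 2 | 6 | 1 |
| Day 2 to 6 | Day 3 to 7 | 5 to 1 | 2 to 6 |
| Day 7 or later, before Visit 2 | Day 8 or later | 0 | 7 |

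The convention is that the day of the goal text counts as untreated. If goal setting itself counts as exposure, a start within the week loses one more day (a Day 1 start leaves 0, a Day 7 start leaves 6). The range stays 0 to 7.

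**4. Does any section choose a row?**
- Table 5.3 read literally with 6.1 points to the first row: goal at Consent, reminder the next morning. The only item that the table labels as baseline, the Baseline Survey, is also at Consent.
- The Consent mark may instead be only the REDCap anchoring question of 10.1. The activity calendar described just before that question is marked at Consent too.
- Section 10.1 puts consent, the goal question and the first wear week under one Visit 1 heading, whereas 5.3 separates Consent from Visit 1. It calls the week an initial assessment and does not say that NUDGE is off.
- The 4.5-month ceiling on NUDGE equals total participation, so no lead-in is set aside. It is only a ceiling, so it does not exclude one.

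No row is fixed.

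**5. Effect of starting after the wear week.** For a first message on Day 8:
- Delay against a Day 1 start: 8 - 1 = 7 days. Against a Consent start: 12 to 18 days, depending on the consent day and on whether a Day 0 is counted.
- Interval to Visit 3 now, from a Day 1 start: 90 - 1 = 89 to 97 - 1 = 96 days.
- From Day 8 with visits unmoved: 90 - 8 = 82 to 97 - 8 = 89 days.
- From Day 8 with later visits moved 7 days (Visit 3 at Day 97-104): 89 to 96 days again.
- Three months is about 91.3 days.
- Consent at Day -10 to Day 104 is at most 114 days, about 3.7 months, against about 137 days in 4.5 months.

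**The case against.** The best defence is that this is a missing sentence and not a flawed design. Change from baseline to post-treatment, together with an initial seven-day assessment, fits an untreated first week. The quoted line of 6.1 gives only the lag from first goal to first reminder and names no study day. The Consent mark is readily explained by the REDCap question. The information letters, which include study calendars, are not in view and may state the start day. Section 10.1 also says that participant contact is described in Section 5.0, where the available text is short, so some content may have been lost. Goals are tied to the last self-monitored value, which suggests gradual change and perhaps little effect in the first week. The message-based feasibility measure and the baseline HbA1c taken from records do not depend on Day 1-7.

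Most of this stands, and it limits the claim. A reader might infer that messaging starts at Consent and that every baseline is contaminated. The documents do not support that: it is one reading of the Consent mark, and a clean baseline may well be intended. A reader might also want a figure for the lost effect. None can be derived, because nothing says how quickly NUDGE acts and medium is given no number.

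The defence does not supply a start day. Intent cannot be executed from 5.3, 6.1 and 10.1 as written, and a literal reading of 5.3 with 6.1 puts NUDGE ahead of the wear week. Dated message records, if kept, could show which days were exposed, but could not restore an untreated level where all seven were.

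**Conclusion.** The point holds as a gap in the plan that can compromise the only efficacy contrast. Following the text can leave 0 to 7 of 21 device days untreated, depending on a start day that is not stated. This rests on Day 1-7 being the only candidate device baseline, which follows from the wear schedule, and on messaging still running at Visits 2 and 3.

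Early exposure would probably reduce the measured change. That assumes NUDGE raises activity early; season, time trend and device reactivity are uncontrolled, so the net direction of error is uncertain. This mechanism alone would not create apparent efficacy where there is none, so it does not support reading a positive result as spurious. The consequence is limited to MVPA and sedentary behaviour and to the larger-study planning that uses them. It should be fixed, with medium confidence, because the start day may be settled in material not available here.

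**What to change.** Reconcile 5.3, 6.1 and 10.1 so that:
- the first actigraph and actiwatch week is completed before the first NUDGE message;
- the bot's start day is stated relative to that week;
- that week is defined, in 4.1 and 27.1 as well, as the baseline for MVPA and sedentary behaviour;
- the text says whether the Consent mark for PA Goal Set is only the REDCap anchoring question.

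If NUDGE must run in that week, report that the estimate is not a change from an untreated baseline.

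**Cost.** If a start after Day 7 is already intended, this is a clarification of the text. Otherwise messaging begins about 7 days later than a Day 1 start, or 12 to 18 days later than a Consent start. Either way it needs an IRB modification and matching edits to the information-letter calendars, but no added visits, devices or participants.

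The trade-off is follow-up time. With visits unmoved, a Day 8 start leaves 82-89 days to Visit 3, short of about 91 days, so the sponsor should check this against the three-month aim in 5.1. Moving the later visits by about 7 days restores the 89-96 days that a Day 1 start gives now, still straddling 91, and stays within the 4.5-month participation. Messaging time available within 4.5 months falls to about 3.9-4.1 months (119-125 of 137 days).
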